	Statistical comparison will be made between the change from baseline at each time point between the Groups 1 and 3 (extensive metabolizers) versus Groups 2 and 4 (poor metabolizers) for each treatment (AT -10 and Clopidogrel).
	The incidence of signs of bleeding from the abbreviated physical examination and the incidence of abnormal liver function tests (ALT, AST, total bilirubin, and alkaline phosphatase) will be tabulated for the treatment groups. The incidence of these events will not be formally tested and the comparison will be observational only. The observational comparisons will be made between the AT -10 and Clopidogrel in the extensive metabolizers and poor metabolizers.
	Pharmacokinetics:
	Pharmacokinetic parameters (AUCt, AUCinf, Cmax, tmax, t¼, kel, Cl/F, Vd/F) will be estimated following noncompartmental analysis of plasma concentration time-course data for Clopidogrel, AT -10 (2-oxo-clopidogrel), and MP-H4. PK parameters at steady-state will be estimated for Clopidogrel, AT-10 (2-oxo- clopidogrel), and MP-H4. Statistical comparison of the single-dose and multiple-dose PK parameters of peak (Cmax) and total (AUCt, AUCinf) exposure for the AT-10 and MP-H4 will be made between the AT-10 and Clopidogrel dose groups; between and within metabolizer groups.
	Although this is not a bioequivalence study following PK comparison will be made:
	• PK comparisons will be made for AT -10 and MP-H4 from AT -10 treatment in extensive metabolizers versus Clopidogrel treatment in extensive metabolizers
	• PK comparisons will be made for AT -10 and MP-H4 from AT -10 treatment in poor metabolizers versus Clopidogrel treatment in poor metabolizers
	• PK comparisons will be made for AT -10 and MP-H4 from AT -10 treatments in extensive metabolizers versus AT -10 treatments in poor metabolizers.
	Other PK comparison will be made if deemed appropriate
Safety Assessment	Tolerability and safety will also be assessed.
	Safety assessments will include screening, pre-dose and post-dose vital signs, ECGs, clinical laboratory testing (hematology, blood chemistry, and urinalysis), documentation of AEs and clinical examinations. Coagulation parameters (PT and PTT) will also be assessed at screening, at housing during each period, at 8 hrs post-dose on each dosing day and at exit or early termination.

Page 17 of 74

Ipca Laboratories Ltd Version 1.0 (Amendment 3.0)

[figure not shown]

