Because clinical trials are conducted under widely varying conditions and durations of follow up, adverse reaction rates observed in the clinical trials of a drug cannot be directly compared to rates in the clinical trials of another drug and may not reflect the rates observed in practice.

Plavix has been evaluated for safety in more than 54,000 patients, including over 21,000 patients treated for 1 year or more. The clinically important adverse reactions observed in trials comparing Plavix plus aspirin to placebo plus aspirin and trials comparing Plavix alone to aspirin alone are discussed below.

Bleeding

CURE

In CURE, Plavix use with aspirin was associated with an increase in major bleeding (primarily gastrointestinal and at puncture sites) compared to placebo with aspirin (see Table 1). The incidence of intracranial hemorrhage (0.1%) and fatal bleeding (0.2%) were the same in both groups. Other bleeding events that were reported more frequently in the clopidogrel group were epistaxis, hematuria, and bruise. The overall incidence of bleeding is described in below table (CURE Incidence of Bleeding Complications (% patients)).

		Plavix (+ aspirin)* (n=6259)	Placebo (+ aspirin)* (n=6303)
		3.7 ‡	2.7 §
leeding		2.2	1.8
		0.2	0.2
globin drop	2	0.9	0.9
rgical interv	vention	0.7	0.7
strokes		0.1	0.1
otropes		0.5	0.5
nsfusion (≥	≥4 units)	1.2	1.0
ling		1.6	1.0
abling		0.4	0.3
ding with		0.05	0.03
oss of visio	m		
nits of bloo	bd	1.3	0.9
		5.1	2.4
therapies we	ere used as approp major bleeding.	5.1	

Major bleeding event rate for Plavix + aspirin was dose-dependent on aspirin: <100 mg = 2.6%; 100-200 mg = 3.5%; >200 mg = 4.9% Major bleeding event rates for Plavix + aspirin by age were: <65 years = 2.5%, ≥65 to <75 years = 4.1%, ≥75 years = 5.9%

Major bleeding event rate for placebo + aspirin was dose-dependent on aspirin: <100 mg = 2.0% 100-200 mg = 2.3%; >200 mg = 4.0% Major bleeding event rates for placebo + aspirin by age were: <65 years = 2.1%, ≥65 to <75 years = 3.1%. ≥75 years = 3.6%

Led to interruption of study medication.

Ninety-two percent (92%) of the patients in the CURE study received heparin or low molecular weight heparin (LMWH), and the rate of bleeding in these patients was similar to the overall results.

COMMIT

In COMMIT, similar rates of major bleeding were observed in the Plavix and placebo groups, both of which also received aspirin (below table: Incidence of Bleeding Events in COMMIT (% patients)).

CONFIDENTIAL

Page 28 of 74

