Ipca Laboratories Ltd Version 1.0 (Amendment 3.0)

Type of bleeding	Plavix (+ aspirin) (n=22961)	Placebo (+ aspirin) (n=22891)	p-value
Major* noncerebral or cerebral bleeding**	0.6	0.5	0.59
Major noncerebral	0.4	0.3	0.48
Fatal	0.2	0.2	0.90
Hemorrhagic stroke	0.2	0.2	0.91
Fatal	0.2	0.2	0.81
Other noncerebral bleeding (non-major)	3.6	3.1	0.005
Any noncerebral bleeding	3.9	3.4	0.004

* Major bleeds were cerebral bleeds or non-cerebral bleeds thought to have caused death or that required transfusion.

** The relative rate of major noncerebral or cerebral bleeding was independent of age. Event rates for Plavix + aspirin by age were: <60 years = 0.3%, ≥60 to <70 years = 0.7%, ≥70 years = 0.8%. Event rates for placebo + aspirin by age were: <60 years = 0.4%, ≥60 to <70 years = 0.6%, ≥70 years = 0.7%.

CAPRIE (Plavix vs. Aspirin)

In CAPRIE, gastrointestinal hemorrhage occurred at a rate of 2.0% in those taking Plavix vs. 2.7% in those taking aspirin; bleeding requiring hospitalization occurred in 0.7% and 1.1%, respectively. The incidence of intracranial hemorrhage was 0.4% for Plavix compared to 0.5% for aspirin.

Other bleeding events that were reported more frequently in the Plavix group were epistaxis and hematoma.

Other Adverse Events

In CURE and CHARISMA, which compared Plavix plus aspirin to aspirin alone, there was no difference in the rate of adverse events (other than bleeding) between Plavix and placebo.

In CAPRIE, which compared Plavix to aspirin, pruritus was more frequently reported in those taking Plavix. No other difference in the rate of adverse events (other than bleeding) was reported.

Post-marketing Experience

The following adverse reactions have been identified during post-approval use of Plavix. Because these reactions are reported voluntarily from a population of an unknown size, it is not always possible to reliably estimate their frequency or establish a causal relationship to drug exposure.

- Blood and lymphatic system disorders: Agranulocytosis, aplastic anemia/pancytopenia, thrombotic thrombocytopenic purpura (TTP), acquired hemophilia A
- Gastrointestinal disorders: colitis (including ulcerative or lymphocytic colitis), pancreatitis, stomatitis, gastric/duodenal ulcer, diarrhea
- General disorders and administration site condition: FeverHepato-biliary disorders: Acute liver failure, hepatitis (non-infectious), abnormal liver function test

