6 STUDY OBJECTIVES AND RATIONALE

6.1 STUDY OBJECTIVES

Primary:

- To determine the safety and tolerability of AT -10 compared to Clopidogrel administered orally to humans.
- To compare effect of AT -10 (loading and maintenance doses) Vs approved doses of Clopidogrel (loading and maintenance doses) on platelet aggregation in poor and extensive metabolizers.
- To confirm the AT -10 loading dose (PD equivalent dose to the Clopidogrel 300 mg) and the AT -10 maintenance dose (PD equivalent to the Clopidogrel 75 mg) given as a loading dose followed by 5 days of maintenance dose

Secondary:

• To determine the single and multiple dose pharmacokinetics (PK) of Clopidogrel, AT -10, and active metabolite MP-H4.

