All subjects who receive at least one dose of the study drug will be included in the safety analysis.

Vital Signs & Wellbeing:

Vital signs (sitting blood pressure, pulse rate, respiratory rate and oral temperature) and wellbeing will be assessed at following time-point.

- Screening
- Housing (both periods)
- Day 1 to 6 (both periods): Pre-dose, 03.00, 06.00 and 10:00 hours of IP administration
- Day 7 at Discharge (both periods)

All these vital signs and well-being assessment will be completed within ± 01.00 hour of the scheduled time so as not to interfere with scheduled blood sampling times or meals. The actual time of measurement will be recorded in the CRF.

CONFIDENTIAL

Page 53 of 74

Ipca Laboratories Ltd Version 1.0 (Amendment 3.0)

Abbreviated Physical Examination:

Abbreviated physical examination focused on signs of bleeding including but not limited to echymosis, petechiae, and bleeding gums will be carried out as a part of clinical examination at screening, housing, discharge and end of study safety assessment as well as on day 1 to 6 (both periods) at 2, 4, 8, 12 hr of IP administration.

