14.4 PHARMACODYNAMIC EFFECT ANALYSIS

ADP induced platelet aggregation will be assessed for change from baseline in each treatment group at each time point assessed on each dosing day (0.5, 2 and 6 hours post dose) and 24 hrs post dosing of last dosing day in each period. The change over time for each parameter will also be assessed.

Platelet inhibition will be calculated as per below formula.

Platelet Inhibition = $(1 - \text{Residual Impedance} / \text{Baseline Impedance}) \times 100$

The results will be reported as either residual platelet aggregation, measured as maximal amplitude of impedance (ohms), or platelet inhibition. The data from treatment groups 1 and 3 will be combined in the CONFIDENTIAL Page 63 of 74

analysis and similarly for treatment group 2 and 4 will be combined in the analysis. Statistical comparison will be made between the change from baseline at each time point between the treatment groups 1 and 3 (extensive metabolizers) versus treatment groups 2 and 4 (poor metabolizers) for each treatment (AT -10 and Clopidogrel). If applicable, as clinical phase of study will be conducted in group of volunteers not more than 18, volunteer group effect will also be analyzed statistically.

The incidence of signs of bleeding from the abbreviated physical examination and the incidence of abnormal liver function tests (ALT, AST, total bilirubin, and alkaline phosphatase) will be tabulated for the treatment groups. The incidence of these events will not be formally tested and the comparison will be observational only. The observational comparisons will be made between the AT -10 and Clopidogrel in the extensive metabolizers and poor metabolizers.

Additionally, the relationship between the PK of MP-H4 and pharmacodynamic measurements will be addressed using population PK-PD analysis.

CONFIDENTIAL

Page 64 of 74

Ipca Laboratories Ltd Version 1.0 (Amendment 3.0)

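### The one AT-10 versus clopidogrel bleeding comparison that the protocol names counts only examination findings, so bleeding recorded solely as an adverse event stays out of it

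*Protocol*

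**What the plan says.** Section 6.1 gives as the first primary objective "To determine the safety and tolerability of AT -10 compared to Clopidogrel administered orally to humans".

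Section 14.4, repeated in the synopsis, states what is tabulated for bleeding: "The incidence of signs of bleeding from the abbreviated physical examination and the incidence of abnormal liver function tests". The synopsis adds "The incidence of these events will not be formally tested and the comparison will be observational only". The contrast is then named: "The observational comparisons will be made between the AT -10 and Clopidogrel in the extensive metabolizers and poor metabolizers".

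Section 11.1 describes the examination as focused on "signs of bleeding including but not limited to echymosis, petechiae, and bleeding gums will be carried out" at screening, housing, discharge and end of study, "as well as on day 1 to 6 (both periods) at 2, 4, 8, 12 hr of IP administration".

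Section 5 describes the bleeding seen with clopidogrel. For CURE it says that major bleeding was mainly gastrointestinal and at puncture sites, and "Other bleeding events that were reported more frequently in the clopidogrel group were epistaxis, hematuria, and bruise". For CAPRIE it says "Other bleeding events that were reported more frequently in the Plavix group were epistaxis and hematoma".

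Adverse events are captured separately. Section 12.1.1 requires all of them to be documented whatever their relationship to treatment, and Section 11.1 puts every dosed subject in the safety analysis. No section adds bleeding adverse events to the tabulation in Section 14.4.

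**The concern.** When a protocol names the data source for a comparison, an analysis plan that follows it inherits the restriction. Here the source is narrower than the outcome of interest. An examination for visible signs will find bruising, petechiae and gum bleeding. It will not see gastrointestinal bleeding, and it will miss a nosebleed that starts and stops between time points. Such events have a place in the adverse event record but none in the bleeding table.

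Bleeding is one of the two serious reactions that Section 5 lists for clopidogrel, and the table is the only place where the protocol sets bleeding on the two drugs side by side. Counts will be small, so leaving out one or two bleeds could change how the table reads.

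**Working it through.** The protocol states no figure for this outcome, and Section 8 says that the sample size is not calculated from a PD effect or PK variability. The check is therefore of coverage and of how sparse the counts will be.

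1. **Examinations per period** (Section 11.1). Dosing days give 6 × 4 = 24. Housing and discharge bring this to 26.

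2. **Overnight gap.** The last examination of a dosing day is at 12 h. The next is 2 h after the following dose, at 24 + 2 = 26 h. The gap is 26 − 12 = 14 h, on five nights (Day 1 to Day 6).

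3. **Washout gap** (minimum 14 days from last dose to first dose, per the synopsis). The last Period 1 dose is on Day 6. The first Period 2 dose is on study day 6 + 14 = 20, and housing is on day 19. From Day 7 discharge to housing is 19 − 7 = 12 days. As a check on the timeline, the last sample falls on day 20 + 6 = 26; adding the housing day before Day 1 gives 27, which matches the stated minimum of 27 days.

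4. **Residual effect within that gap.** Section 5 gives recovery in about 5 days and an affected-platelet lifespan of about 7 to 10 days. Counted from Day 6, the effect ends on day 11 by the first figure and on day 13 to 16 by the second. The unexamined days with residual effect are 11 − 7 = 4, or 13 − 7 = 6 to 16 − 7 = 9.

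5. **Sparse counts.** The first AT-10 study, summarised in Section 5, had 1 of 30 subjects with ecchymosis and no other bleeding signs. Take 1/30 as the rate:
   - n = 20 (one metabolizer group): expected 20/30 = 0.67; chance of none (29/30)^20 = 0.51.
   - n = 40: expected 40/30 = 1.33; chance of none (29/30)^40 = 0.26.

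   That rate is per subject in a crossover, and the protocol does not say which drug was involved, so the per-drug expectation could be lower.

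6. **Size of the under-count, by assumption only.** The share of bleeding visible at examination is not given anywhere. Suppose 10% of subjects bleed on a drug:

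| Share visible at examination | Expected in table, n = 20 | Expected in table, n = 40 |
|---|---|---|
| 25% | 0.5 | 1 |
| 50% | 1 | 2 |
| 75% | 1.5 | 3 |
| 100% | 2 | 4 |

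7. **Urinalysis timing** (Sections 9.2 and 11.1). Urine is tested at screening, housing and end of study. Day 7 lists hematology, liver tests and coagulation, but no urine. For the Period 2 drug the first test after dosing is at discharge, about 1 day after the last dose. For the Period 1 drug it is at Period 2 housing, 19 − 6 = 13 days after the last dose. The two windows are not comparable.

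**The case against.** The best case against this point has four parts.

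- **The rule is not exclusive.** Section 14.4 says that examination signs are tabulated. It does not say that bleeding is compared from no other source. Adverse event tables are usually left to the analysis plan, which is not shown and may summarise bleeding terms by drug. This stands as a limit: the absence of an adverse event table is not the finding. But the named bleeding comparison still has one source, and nothing in the protocol widens it.

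- **The examination is open-ended.** Its three signs are examples, so a nosebleed in progress at an examination could count, and a washout bruise still visible at Period 2 housing could be recorded there. This stands. What remains outside is bleeding known only from an adverse event report.

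- **The gaps are less bare than they look.** Subjects stay in the facility throughout dosing, adverse events are monitored every day, and vital signs and wellbeing are checked before each dose and at 3, 6 and 10 h. Bruises and petechiae rarely vanish overnight. This stands, so the overnight gap matters only for brief bleeds, which would go to the adverse event record. The washout gap is less well covered.

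- **The setting differs from CURE.** Those patients took aspirin and most also had heparin. Here the subjects are healthy, aged 18 to 45, and screened for bleeding risk and recent aspirin or NSAID use. The types of bleeding are relevant, but the rates do not transfer.

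A reader might also infer that these bleeds go unrecorded, or that the table favours one drug. The documents support neither. Adverse events are documented for everyone dosed. In a crossover with the same examination schedule on both drugs, an under-count on both does not by itself distort the comparison.

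**Conclusion.** The point holds as a definition that is too narrow. The only bleeding comparison that the protocol names draws on examination findings alone, while other bleeding is collected and left out. The result is an under-count of unknown size in a descriptive table. An examination-only count can equal the all-source count or fall below it, but cannot exceed it.

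The firm figures are the roughly 12 unexamined washout days, of which 4 to 9 carry residual effect, and the 14-hour overnight gap. Both assume the minimum washout and the examination times as written. The table in the working is an illustration with assumed rates.

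No conclusion about direction between drugs follows, no data are lost, and sample size, power and error rates are untouched because the comparison is not tested. The change is worth making because comparative safety is a primary objective and expected counts are near zero or one per group, so a single omitted bleed is visible.

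**What to change.** In Section 14.4 and the synopsis, define the tabulated outcome as subjects with any bleeding found at the abbreviated examination or reported as an adverse event, each subject counted once per drug, within each metabolizer group. Then:

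- show the examination-only count as a subset, so the present table is kept;
- list puncture-site and cannula-site bruising separately from other bleeding;
- assign bleeding that starts after Period 1 dosing and before the first Period 2 dose to the Period 1 drug;
- show blood in urine as its own line by period and do not pool it with the rest, because urinalysis is not scheduled at Period 1 Day 7.

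The comparison stays observational. The cost is a wording change, one extra table from data already collected, and slightly higher counts. No extra visits, samples or examinations are needed.

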15 ETHICAL AND REGULATORY STANDARDS

15.1 ETHICAL PRINCIPLES, LAWS AND REGULATIONS

The clinical study will be conducted as per the principles and requirements of Declaration of Helsinki (Ethical principles for medical research involving human subjects, revised by the 64th WMA General Assembly, Brazil, 2013), and are consistent with the ICH-GCP (E6-R2) guidelines along with the local regulatory requirements of GCP for Clinical Research In India (2004, CDSCO), New Drugs and Clinical Trials Rules 2019 and all applicable amendments (Drug and Cosmetics Rules, 1945) and ICMR's National Ethical guidelines for Biomedical and Health Research involving Human Participants (2017).

15.2 ETHICS COMMITTEE

Protocol (protocol amendment, if applicable) and associated documents will be reviewed by Ethics Committee (EC), Registered with CDSCO, for the formal approval of the study conduct. The decision of the EC signed by its chairman / designed person of EC with EC composition, concerning the conduct of the study will be made in writing to the investigator and a copy of this decision will be provided to the sponsor before commencement of this study. If requested, a progress report during the study and a summary of the study at the end of the clinical study will be sent to the EC. The study will not commence until the committee has approved the final version of the protocol.

15.3 INFORMED CONSENT PROCESS

The investigator or a person designated by the investigator, and under the investigator's responsibility, should completely inform the subjects and/or their families describing this study and providing sufficient information to them for making an informed decision about their participation in this study.

[figure not shown]
All the subjects should be informed to the complete extent possible about the study, in language and terms they are able to understand. Consent form must be EC approved and the subject will be provided the consent in vernacular language of his /her choice(s).

Prior to subject's participation in this study, the written informed consent form must be signed, name filled in and personally dated by the subject / impartial witness (along with subject's thumb impression in case when he/she is illiterate) and by the person who conducted the informed consent discussion. A copy of the signed and dated written informed consent form will be provided to the subject.

Subjects may be paid an adequate (EC approved) participation fee on account of their participation in the study. In case of withdrawal of a subject before completion of the study, subject will be paid compensation corresponding to the extent of participation and any controversy pertaining to this will be forwarded to EC and the decision of EC will be final as well as binding on both the subjects and CBCC Global Research LLP.

CONFIDENTIAL

Page 65 of 74

As per New Drugs and Clinical Trials Rules 2019, audio-video recording of the informed consent process is not applicable for this study.

15.4 SUBJECT AND DATA CONFIDENTIALITY

Subject confidentiality along with the information disclosed/provided/produced by the sponsor during the clinical study, including, but not limited to, the clinical study protocol, the CRFs, ICFs and results are strictly held in trust by the sponsor, sponsor's authorized personnel, investigator and their staff members, CBCC and its staff. No information concerning the study or the data will be released to any unauthorized third party without prior written approval of the sponsor.

The study monitor or other authorized representatives of the sponsor may inspect all documents and records maintained by the investigator and pharmacy records for the subjects in this study. The clinical study site will permit access to such records.

However, the submission of this clinical study protocol and other necessary documentation to the ethics committee (EC) is expressly permitted, the EC members having the same obligation of confidentiality.

16 RECORD RETENTIONS

It is the responsibility of Sponsor to make arrangements for safe and secure custody of all study related documents and material for a period of 15 years after the completion of the study. These documents should be retained for a longer period of time, if required by an agreement with the sponsor. In such an instance, it is the responsibility of the sponsor to inform the investigator / institution as to when these documents no longer need to be retained. The Bioanalytical, data will be archived at Bioanalytical site.

Ipca Laboratories Ltd Version 1.0 (Amendment 3.0)

